9.2 Justification for dose

Not applicable

9.3 Trial population

The infants participating in this trial will have no known hearing loss, having either passed newborn hearing screening or diagnostic audiological assessment.

9.4 Eligibility criteria

9.4.1 Inclusion criteria

Each infant must meet all of the following criteria to be enrolled in this trial:

- Is between the ages of 1 and 24 months at the time of fNIRS testing.
- Has no known hearing loss, having either passed newborn hearing screening or diagnostic audiological assessment.
- Has a legally acceptable representative capable of understanding the informed consent document and providing consent on the participant’s behalf.

9.4.2 Exclusion criteria

Infants with skin conditions such as cradle cap, eczema, or other skin conditions will be excluded.

There are no additional exclusion criteria other than not meeting the inclusion criteria.

9.5 Lifestyle considerations

Not applicable

9.6 Screen failures

Screen failures are defined as participants who consent to participate in the trial but who are found, during the screening procedures, to be ineligible to continue in the trial. Since the screening process only consists of establishing from the parent the age and normal hearing status of the infant, the screening and consenting process is usually rolled into one event.

9.7 Recruitment and identification of potential participants

Recruitment of infants and their parents/guardians

Infants and their parents/guardians will be recruited through any of the following means:

- Social media and the Bionics Institute website
- Word of mouth

For recruitment via social media etc, advertisement will take place through Bionics Institute website, social media platforms Facebook and Instagram, online platforms such as the University of Melbourne staff noticeboard, and relevant notice boards etc e.g., maternal and child health centres, early learning centres, and other relevant community centres. We do not expect any difficulty recruiting 10 infants based on our current recruitment rate for other studies.

9.8 Consent

Written consent will be obtained using a face-to-face process and a paper consent form. Since all the infant participants will be under 2 years of age, consent will be sought from their parent/guardian.

The investigator or delegated member of the trial team will discuss the trial with the parent/guardian and will provide them with the Participant Information and Consent Form (PICF), which will describe the purpose of the trial, eligibility for inclusion, the procedures to be followed, and the risks and benefits of participation.

The investigator will conduct the informed consent discussion following confirmation of eligibility and will check that the parent/guardian comprehends the information provided. The investigator will answer any questions about the trial.

The parent/guardian will be invited to provide written consent. Consent will be voluntary and free from coercion.

The investigator who conducted the consent discussion will also sign the informed consent form. A copy of the consent form will be given to the parent/guardian.

At any point, parents/guardians can withdraw from the project with no consequences. Testing can be stopped at any stage should the parent/guardian not wish to proceed further.

10 INTERVENTION

10.1 Treatment arms

All infants undergo fNIRS testing using the EarGenie MVP

10.2 Trial Intervention(s)

10.2.1 Description of trial investigational products

10.2.1.1 EarGenie MVP

Product name	EarGenie MVP
Device Type	Continuous wave near-infrared spectroscopy (NIRS) imaging system

Please see Investigator's Brochure for further engineering design details and safety features.

The device runs two automated tests to measure sound detection and discrimination in sleeping infants. The device plays speech sounds, either through a loudspeaker, or via tubephones, at user-defined intensities, durations and timing. It has a user interface on a dedicated computer that enables a clinician to check the sound calibration and optode function before a test starts. Sound calibration involves using a sound level meter to measure the sound being output by the device. These sound measurements are routinely made by the research audiologist when setting up for the test, when the infant is not present. Optode function checking is initiated by the user in the graphical user interface (GUI) and involves automatic adjustment, within safe limits, of the intensity of light being emitted by the light emitting diodes (LEDs) so that the detectors are operating within an optimal range. The user interface also presents information about the test being run, such as a raw data stream and progress of the on-line analysis. After the test is complete it outputs a test report indicating whether the infant heard the sounds and/or discriminated between the sounds presented, along with a confidence estimate and data quality statement. See Section 12.3 for details of the test protocol in this project. Section 12.3 describes the specific sounds to be used in this project for device feasibility testing ("ba" and "ga") and their durations (repeated 5.4 s).

11 RANDOMISATION AND BLINDING

11.1 Concealment mechanism

All infants undergo fNIRS testing so there is no randomisation or blinding for them or their parents/guardians.

11.2 Breaking of the trial blind

NA.

12 TRIAL VISITS AND PROCEDURES

12.1 Trial timeline

Each infant will have a single fNIRS test.

12.2 Schedule of assessments

The schedule of interventions for infants (Time is relative to enrolment)

	Enrolment	fNIRS test session 1
TIME POINT	Day 1	within 4 weeks
ENROLMENT:		
Eligibility screen	X	
Informed consent		X
INTERVENTIONS:		
Otoscopy and tympanometry		X
fNIRS tests		X

12.3 Description of procedures

Screening for eligibility

Determination of infant eligibility will be undertaken by confirming that the infant has passed hearing screening or diagnostic audiological assessment and is under the age of 2 years. The infant will be assigned an anonymising code.

The fNIRS test session

Before completing the fNIRS tests, the infant will undergo otoscopy and tympanometry to exclude possible temporary conductive hearing loss associated with abnormal tympanometric results. These are standard audiological procedures. If the infant has abnormal tympanometric results in both ears on the day, the test session will be terminated. The parent/guardian will be advised of the finding and its possible consequences (possible conductive hearing loss, possible progression to acute otitis media) and advised to seek medical advice should the infant show signs of illness or if hearing loss is suspected.

All assessments in the fNIRS test session will be undertaken by qualified paediatric audiologists who are trained in the fNIRS procedures.

For the fNIRS tests, the infant will be asleep. The appointment will be scheduled to just before their usual daytime nap time to make it easier to get the infant to sleep. The parent will guide the getting-to-sleep process.

After the infant is asleep, the headgear will be placed on the infant's head and optode calibration procedure is undertaken to ensure the equipment is ready. During the actual test, blocks of speech sounds lasting 5.4 seconds will be played to the infant either via tubeophone or via speakers at a comfortable level (65 dB SPL). Tubephones are sound transducers that are inserted in the ear and are used in standard audiological testing of infants. Testing will usually proceed for the duration of the infant's sleep period (usually around 40 minutes). If the infant remains asleep after the main fNIRS tests are completed (detection of "Ba" at 65 dB SPL, and discrimination of "Ba" from "Ga"), further speech sounds will continue to be played at levels within the comfortable loudness range until the baby wakes. The responses to those additional sounds will not be used in the main study outcome analysis of preliminary functionality (Section 16) but will provide additional support for this. Leaving the headgear on and functioning for the duration of the infant's sleep cycle (around 40 minutes) is important for obtaining the safety and comfort information.

Our outcome measures for device feasibility are the incidence of detection and discrimination responses obtained. Specifically, we expect that at least 9/10 infants (90%) will show a significant detection response for “Ba” at 65 dB SPL, and that their average waveforms for this test should consist of a positive HbO peak around 5-8 s latency, or a negative HbO response with latency 12-16 s, or a shape consistent with a combination of these shapes (refer to Figure 1). For the test of discrimination of “Ba” from “Ga”, we expect that at least 7/10 infants (70%) will show a significant discrimination response, and that their average response waveforms should consist of a positive HbO response with latency 6-12 s or a negative HbO response with latency 12-20 s, or a combination of both these shapes (Figure 2).

During the test session, the infant will be monitored for any signs of discomfort or distress, and after the session. The measures of discomfort will include observations of crying, attempts to remove headgear, verbal indications of distress (in an infant with developed speech), and, after the test, observations of any marks left by the headgear on the skin, along with the duration (in minutes) of such incidents. The infant’s skin will be examined to detect any signs of skin reaction or areas affected by too much pressure of the head gear. If any distress or skin reactions occur in the test session, the parents will be contacted in the following 48 hours to document whether the problem resolved and how long it took. Any comments provided by the parents within 48 hours of the test re any potential side effects noticed will be recorded. All of this information will be documented on the Case Report Form. All Case Report Forms will be collated and summarised in a final report re safety, along with any recorded adverse events.

Adverse events: Since fNIRS tests are considered to be non-invasive and safe, we do not anticipate any serious adverse events. However, if an adverse event occurs, the ethics committee will be informed if required by their procedures, and the standard procedures of the Bionics Institute will be followed (see Section 13).

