Description of Interventions	
Each infant will have functional near-infrared spectroscopy (fNIRS) performed using EarGenie MVP, to measure changes in cortical blood oxygenation in response to increased neural activity during sound detection and discrimination.
 
During testing, which is performed during natural sleep, the infant wears the custom-made headgear while sounds are presented either through tube-phones or via a loudspeaker.
 
The infant will be presented with different speech sounds at 65 dB SPL. The device runs two automated tests, one to measure whether the baby detected the sound and the other to test whether the

Title: EarGenie minimum viable product (MVP)

Protocol Number: 98058

Version & date: version 3, dated 15 September 2023

Page 5 of 31

	
baby discriminated between two different speech sounds (“Ba” and “Ga”). The sound levels used are not hazardous to the individual.
 
The headgear comprises a soft material headband and a detachable, Bluetooth-enabled, battery-powered montage. The montage is made up of a flexible printed circuit board, flat-surfaced optical LED emitters and detectors and a flexible montage cover.
 
The montage is positioned so that the sensors are located over the regions of the brain that process sound and language. Near infrared light, with 740 nm and 860 nm centre wavelengths, travels from each emitter through the scalp and underlying cortical brain tissues. The detectors measure that portion of the light that is transmitted back to the scalp (the rest being harmlessly absorbed or scattered) and, from these optical measurements, changes in oxygenated and de-oxygenated haemoglobin concentrations are calculated. Changes in these measures that are time locked to the presentation of sound, or a change of sound, provide an index of sound detection and discrimination, respectively.
 
The EarGenie MVP device is controlled using a graphical user interface running on a laptop computer, which allows the user to control sound presentation, visualise optical measurements and obtain the results of our patented, automated response-detection algorithm in real time.

Trial Duration	6 months or until 10 infants have been tested, whichever is shorter
Participant Duration	Infants will have just one test session, which typically takes around 2 hours.

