16.3 Methods of analysis

Safety analysis: A careful recording during all of the 10 test sessions of any signs of discomfort from the infant, along with any parent reports of such discomfort within 48 hours of the test, will be noted on Case Report Forms and collated and summarised at the end of the study. Any adverse events will be recorded and managed as per Section 13. The data will be presented as incidence of such events along with their duration, and a full description of each incident.

To obtain preliminary evidence of the functionality of the EarGenie MVP, the automatic reports generated by EarGenie MVP, which includes the test result and the average haemodynamic response waveforms related to that test, will be examined. We expect infants with normal hearing to be able to both hear the speech sounds and to be able to discriminate them. Therefore, we expect a majority of infants to return a positive test result (as in our previous research with the NIRx system), and that the waveforms generated should have characteristics in common with what we expect from our previous research. These data will be summarised as proportions of infants for whom the EarGenie MVP test showed a) a significant detection, and b) a significant discrimination as detailed below.

Specifically, we expect that at least 9/10 infants will show a significant detection response for "Ba" at 65 dB SPL, and that their average waveforms for this test should consist of a positive HbO peak around 5-8 s latency, or a negative HbO response with latency 12-16 s, or a shape consistent with a combination of these shapes (refer to Figure 1).

For the test of discrimination of "Ba" from "Ga", we expect that at least 7/10 infants will show a significant discrimination response, and that their average response waveforms should consist of a positive HbO response with latency 6-12 s or a negative HbO response with latency 12-20 s, or a combination of both these shapes (Figure 2).

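### Leftover sleep time goes on unspecified extra sounds, while no planned run can show a false positive although the secondary outcome claims consistency with the earlier device's specificity

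*Combined protocol and SAP*

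**What the plan says.** Section 12.3 sets two main fNIRS tests: detection of Ba at 65 dB SPL, and discrimination of Ba from Ga. "Testing will usually proceed for the duration of the infant's sleep period (usually around 40 minutes"). For infants who outlast the main tests, "further speech sounds will continue to be played at levels within the comfortable loudness range until the baby wakes". No sound, number, order or exact level is given for these runs. The synopsis mentions one level only: "The infant will be presented with different speech sounds at 65 dB SPL".

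Section 12.3 says the extra responses "will not be used in the main study outcome analysis of preliminary functionality (Section 16) but will provide additional support for this". Its next sentence gives another reason for continuing: leaving the headgear on and functioning for the sleep cycle "is important for obtaining the safety and comfort information".

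Section 16.3 covers the main tests only: "These data will be summarised as proportions of infants for whom the EarGenie MVP test showed a) a significant detection, and b) a significant discrimination". The marks are at least 9 of 10 infants for detection and, for discrimination, "we expect that at least 7/10 infants will show a significant discrimination response", each with a waveform-shape expectation. Nothing in Section 16 mentions the extra runs.

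The synopsis and Section 8.2 define the secondary outcome as results largely consistent with both the sensitivity and the specificity obtained earlier with the NIRx device in normal-hearing infants. Section 6.2 gives those figures: 97% and 100% for detection, 78% and 100% for discrimination.

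**The concern.** Two things look wrong, and they differ in weight.

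The lesser is the wording. Section 12.3 states before any data exist that the extra responses will be supportive. It gives no denominator, no response criterion and no place for absent responses.

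The greater is what the time is used for. A specificity claim needs runs in which the correct answer is no response. In normal-hearing infants these are runs with no sound, or with no change of sound. The plan has none. Both outcome tests present a real stimulus that the infant is expected to hear or discriminate, and so do the extra runs, since they too are speech sounds. A high proportion of positive results therefore shows either a device that responds to the brain signal or one that reports a significant response too readily. The plan's only guard against the second explanation is the waveform-shape expectation. The results are meant to support later trials of the device (Section 21), so the distinction matters.

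**Working it through.** **1. The plan's own marks.** Inputs: reference sensitivities of 97% and 78% (Section 6.2), and 10 infants.
- Detection: 10 × 0.97 = 9.7, rounded down to 9.
- Discrimination: 10 × 0.78 = 7.8, rounded down to 7.

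Both marks in Section 16.3 follow from the reference sensitivities. The reference specificity of 100% enters neither.

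**2. Whether any planned run can give a false positive.**

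| Run | Stimulus | Expected result | Can show a false positive? |
|---|---|---|---|
| Detection of Ba, 65 dB SPL | Real sound | Positive | No |
| Discrimination of Ba from Ga | Real sound change | Positive | No |
| Extra runs (12.3) | Real speech sounds, unspecified | Not stated | Not by design |

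Figure 1's caption shows that the detection stimulus is set against a silence baseline. The documents do not say that silence is scored as a separate test with its own result.

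**3. What the marks cannot separate.** Suppose a true response is present with probability s, and the algorithm wrongly calls a fraction f of the remaining runs significant. The positive rate is then s + (1 − s)f. The documents give neither value for EarGenie. For illustration take s = 0.5, ignore the waveform expectation, and compute the exact binomial probability of at least 7 of 10:
- f = 0: rate 0.50, probability 0.172.
- f = 0.2: rate 0.50 + 0.50 × 0.2 = 0.60, probability 0.382.
- f = 0.4: rate 0.50 + 0.50 × 0.4 = 0.70, probability 0.650.

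False positives make the mark easier to reach, and nothing in the two outcome tests measures f.

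**4. What one fixed control run would show.** With zero positives in n runs, the exact one-sided 95% upper bound on the false-positive rate is 1 − 0.05^(1/n). The documents do not say how long the main tests take or how many infants sleep past them, so n is shown over a range.

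| n | Upper bound if 0/n |
|---|---|
| 10 | 1 − 0.05^(1/10) = 25.9% |
| 8 | 1 − 0.05^(1/8) = 31.2% |
| 6 | 1 − 0.05^(1/6) = 39.3% |
| 5 | 1 − 0.05^(1/5) = 45.1% |
| 3 | 1 − 0.05^(1/3) = 63.2% |

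From the other side, an assumed true false-positive rate of 20% would give at least one positive in 10 runs with probability 1 − 0.8^10 = 0.893. Ten control runs would thus probably reveal a gross fault, but they could not confirm 100% specificity.

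**The case against.** The strongest reply is that the extra runs do no harm. The sentence that calls them supportive also keeps them out of the functionality analysis, and the 9/10 and 7/10 marks are tied throughout to the two named tests. The period also serves the primary safety and comfort outcome, so the time is not wasted. In a ten-infant study that declines formal statistics (Section 16.1), exploratory sounds need little regulation. All of this stands, and it is why the wording is only a minor matter.

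A reader might infer that a narrowly missed mark could be made good by quoting favourable extra responses, or that these data can count only in the device's favour. The documents do not support either reading. The marks exclude the extra runs, nothing permits absent responses to be withheld, and Section 14.2.6 makes individual raw fNIRS data and the stimulus presentation protocol available to approved researchers.

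It can also be said that a no-sound run is a new design element needing ethics committee approval (Section 17.2), and that the documents do not confirm the device can run one. Section 10.2.1.1 describes two automated tests with user-defined intensities, durations and timing, which leaves the question open. Both points are fair, so the proposal is conditional on the software and has an alternative. They do not answer the mismatch in the secondary outcome: the plan names specificity and collects nothing that bears on it.

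**Conclusion.** The point holds as a cheap improvement and a needed match between claim and data. No stated figure is wrong, and neither the marks nor the primary outcome is affected. What the plan lacks is any observation from which a false-positive rate could be seen, although its secondary outcome claims consistency with an earlier specificity of 100%.

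The gain is modest. With all ten infants contributing and no positives, the false-positive rate would be bounded at about 26%; with five contributing, at about 45%. This assumes one independent run per infant. Infants who stay asleep are a subset, so the count describes them and need not represent all ten. The documents do not say how the earlier specificity was measured, so a control run would be descriptive and not a formal comparison.

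**What to change.** 1. In Section 12.3, make the first run after the two main tests one fixed run with no sound, or with no change of sound. Choose one type in advance and use it identically for every infant still asleep. First confirm that the device software can run and score it.
2. In Section 16.3, report positives over all such runs attempted, as a descriptive false-positive count with its upper bound, and state how many infants contributed.
3. If no such run is added, delete *and specificity* from the secondary outcome in the synopsis and Section 8.2.
4. Label any later extra sounds exploratory. List all of them by infant with sound, level and result, whether positive or absent, and remove the statement that they will provide additional support.

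Cost: a small protocol amendment with ethics committee approval, a pre-set run order, a listing, and less time for free-choice sounds. Using sleep time already in the plan adds nothing to the session, and the headgear stays on and functioning as the safety and comfort objective requires. Items 3 and 4 are text changes and a listing only.

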We expect that babies will not experience discomfort from wearing the headgear, which holds the optical emitters and detectors and electronics. It is made up of a headband made from a soft material which is easily fitted on the infant's head using low profile velcro hooks that are easy to adjust and undo. The montage containing the optodes is a flexible, moulded assembly which clips into the headband. The only parts of the headgear that contact the baby's scalp are the head band and the flexible montage cover. There are no cables to hinder movement or cause entanglement.

The headgear can be positioned before the baby is settled to sleep or once they are asleep. Our experience, gained by testing over 100 babies with our research device (NIRx NIRScout) and a cap covering the whole head, is that placement causes only minor disturbance, and that the great majority of babies continue to sleep once it is placed. We reasonably expect that babies will experience less disturbance with this more comfortable headgear than from the NIRx research device.

The case report form for each infant will capture any discomfort or observable effects on the baby's skin as this study's primary outcome measures (along with any unexpected adverse events).

Time and travel

We schedule a 2-hour appointment for the test session and recognise that this is a substantial time commitment for a family with a young baby. As experienced audiologists we are sensitive to this and make every effort to schedule appointments that are convenient for the family. Families are reimbursed their travel expenses and provided with free onsite parking.

Sound levels

Our test protocols use soft to comfortably loud level sounds and do not involve high-level sounds, however it is recognised that there is potential for their accidental presentation due to operator or technical error. To avoid this potential risk, all sounds, which are stored digitally as .wav files, are measured using a calibrated sound level meter at the time that the protocol is developed. On the day of testing the pre-test protocol involves both listening to the sounds and measuring them with a sound level meter to ensure that there are no sound artifacts and that presentation levels are correct.

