12.5.3 Losses to follow-up

Not applicable.

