13.2 Capturing and eliciting adverse event/reaction information

Adverse events will be captured through observation or spontaneous parental report during the infant's session at the Bionics Institute, or if spontaneously reported by their parents up to 48 hours following. Events will be followed until resolution or stabilisation. They will be recorded for each infant on their Case Report Form (CRF).

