16.2.1 Handling of missing data

NA. There is only one test session and if a parent withdraws before or during the session, we will replace that infant with another.

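### Post-session skin reactions and distress are ascertained unevenly: no family is asked about new events, and parents are contacted only after an in-session problem; separately, the described screening omits the skin-condition exclusion.

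*Combined protocol and SAP*

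**What the plan says.** **During the session and at its end.** Section 12.3 has every infant monitored for discomfort or distress. It also says that the infant's "skin will be examined to detect any signs of skin reaction or areas affected by too much pressure of the head gear". Section 7.1 makes these observations primary outcome measures: "The case report form for each infant will capture any discomfort or observable effects" on the skin.

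**After the session.** Section 12.3 sets a condition for contacting the family: "If any distress or skin reactions occur in the test session, the parents will be contacted in the following 48 hours". The purpose follows in the same sentence: "to document whether the problem resolved and how long it took". Section 12.3 adds that comments parents make within 48 hours will be recorded. Section 13.2 gives the adverse-event rule: events are captured during the session, "or if spontaneously reported by their parents up to 48 hours following".

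**In the analysis.** Section 16.3 summarises signs of discomfort recorded in the ten sessions, "along with any parent reports of such discomfort within 48 hours of the test", as incidence, duration and description.

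**Eligibility.** Section 9.4.2 excludes infants with skin conditions and names cradle cap and eczema as examples. Section 9.6 says that screening is confined to age and hearing status. Sections 12.3 (eligibility paragraph) and 12.4.1 list only those two items.

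**The concern.** The primary objective is safety and comfort in a first-in-human study, and its measure is an incidence (section 8.2). An incidence can be read only if each infant had a similar chance of having an event recorded. That holds for the session itself. It does not hold for the 48 hours afterwards, where a family is contacted or not according to what happened in the session, and where even the contacted families are followed up about a problem already known.

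Because section 16.3 brings 48-hour reports into the safety summary, the final report could state that no late reactions were seen when no parent had been asked. Silence and absence of a reaction would look the same.

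The screening point is separate. An exclusion that appears in no described screening step may be applied inconsistently, and pre-existing skin problems make marks on the skin harder to interpret.

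**Working it through.** The plan has no figure to reproduce: section 16.1 gives no sample-size calculation and plans no statistical analysis. The check is mainly a reading of the procedures side by side.

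**Step 1. Who is asked what after the session.**

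| Infant | Contact made by the study team | Stated content | Route for a new late event |
|---|---|---|---|
| Problem in session | Yes, within 48 hours (12.3) | Course of the known problem | Parent volunteers it |
| No problem in session | None described | None | Parent volunteers it (12.3, 13.2) |

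On the text, neither row includes a question about new events. At most, the first row gives the parent an occasion to mention one.

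**Step 2. What a zero count would support.** The inputs are n, the number of families actually asked (at most 10, section 2), and zero late events. The one-sided 95% upper limit p solves (1 − p)^n = 0.05, so p = 1 − 0.05^(1/n).

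- n = 10: 1 − 0.05^(1/10) = 1 − 0.741 = 0.259, or 26%.
- n = 8: 1 − 0.05^(1/8) = 1 − 0.688 = 0.312, or 31%.
- n = 0: (1 − p)^0 = 1 for every p, so no value of p is excluded and there is no limit.

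The last line is the plan as written if all ten sessions are uneventful. The other two lines assume that parents who are asked answer accurately and, for n = 8, that the two families not reached resemble the rest.

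**Step 3. Eligibility text.**

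| Section | Skin condition | Hearing | Age |
|---|---|---|---|
| 9.4.2 Exclusion criteria | Excluded | – | – |
| 9.6 Screen failures | Not listed; list stated as complete | Yes | Yes |
| 12.3 Eligibility paragraph | Not listed | Yes | Yes |
| 12.4.1 Screening questions | Not listed | Yes | Yes |

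The described screening would not apply the exclusion in 9.4.2.

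**The case against.** **The outcome is mostly a session outcome.** The synopsis describes discomfort shown while the device is worn. Section 8.2 counts marks left by the headgear, and section 13.1.1 lists skin irritation or injury remaining after removal. These can largely be seen on the day, in all ten infants. This stands, and it limits the point to late-onset events. Wear lasts around 40 minutes, and section 7.1 reports five years of fNIRS in this laboratory without adverse events, although with other devices. Late reactions may well be rare.

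**Section 12.3 also says that infants are monitored after the session.** It does, without restricting this to infants who had a problem. But no method, duration or contact is attached, and section 13.2, which governs adverse-event capture, relies on spontaneous report. The phrase does not close the gap.

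**No inference is planned.** That is correct. The limits in the working show what a zero would be worth; they are not an error in the plan.

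**The skin exclusion may be applied in practice.** Medical history is collected (section 14.2.1), the information form describes eligibility (9.8), and SOPs are to cover eligibility (15.3). Any of these could bring a skin condition to light. None is described as a check of this criterion, so the wording conflict remains, but a reader should not infer that ineligible infants will be enrolled.

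**Stronger readings that the documents do not support.**

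- A reader might infer that late events will be under-counted by some stated amount. The documents give neither a late-event rate nor a probability of volunteering.
- A reader might treat the families contacted under section 12.3 as a sample asked about late events and compute a limit from them. The stated purpose of that contact is different, so no such limit follows.
- A reader might cite the missing-data statement in section 16.2.1 as denying missingness in the 48-hour window. That section concerns withdrawal before or during the session and does not address the window.
- A reader might infer that skin is not checked before the headgear goes on. No such check is described, but the case report form is not in the reviewed text and may contain one.

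**Conclusion.** The point holds in a limited form. After the session, ascertainment depends on whether the infant had a problem in the session, and no family is asked about new events; yet 48-hour reports enter the primary safety summary. The in-session incidence is sound and is not in question. The size of any late under-count cannot be estimated and may be small. What can be said is that, with no family asked, a zero supports no upper limit, against 26% with all ten reached and 31% with eight, assuming accurate answers and no selection among those reached. This is a cheap improvement to how the primary outcome can be read; it does not invalidate the design.

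The eligibility conflict is a plain inconsistency between section 9.4.2 and sections 9.6, 12.3 and 12.4.1. The criterion itself is clear; the screening description is incomplete.

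**What to change.** 1. In sections 12.3 and 13.2, contact every parent once at about 48 hours with the same short questions on skin and distress, whatever happened in the session. Keep the existing follow-up of known problems.
2. In section 16.3, report the number of families reached and the late events separately from the in-session incidence.
3. Add a skin-condition question to section 12.4.1, and align sections 9.6 and 12.3 with 9.4.2.
4. Optional: if the case report form does not already have one, add a field for the state of the skin under the headgear before placement, to inform the causality grading in section 13.5.

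**Cost.** Ten short calls or messages, one screening question and possibly one form field, with no extra visit. Parents who are asked directly will report some minor unrelated events, which section 13.5 already provides for grading. A changed safety-capture procedure would probably need a protocol amendment and ethics approval under section 17.2.
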